#### 7.4.2.6 Partial Discontinuation of Ipilimumab in the Arm A

Subjects treated with nivolumab and ipilimumab may discontinue ipilimumab and continue to receive nivolumab (ie, partial discontinuation).

The following will be summarized for subjects receiving the immunotherapy in the arm A

- Number and percentage of subjects who had partial discontinuation of ipilimumab.
- Reason for partial discontinuation.

Reason for partial discontinuation will be retrieved from dosing CRF pages.

#### 7.4.3 Concomitant Medications

Concomitant medications, defined as medications other than study medications which are taken at any time on-treatment (i.e. on or after the first day of study therapy and within 100 days following the last dose of study therapy), will be coded using the UMC WHO Drug Global Dictionary.

The following summary table will be provided:

• Concomitant medications (subjects with any concomitant medication, subjects by medication class and generic term)

Prior medications, defined as non-study medications with a start date before consent date, and current medications, defined as non-study medications with a start date before the first date of study medication and stop date after consent date, will be coded using the UMC WHO Drug Global Dictionary.

The following summary table will be provided:

• Prior/current medications (subjects with any prior/current medication, subjects by medication class and generic term)

A by-subject listing will accompany the table.

## 7.4.3.1 Immune Modulating Medication

Immune modulating concomitant medications are medications entered on an immune modulating medication form or available from the most current pre-defined list of immune modulating medications. The list of anatomic class, therapeutic class and generic name used for the selection at the time of the database lock will be provided.

The percentage of subjects who received immune modulating concomitant medication for

- management of adverse event
- premedication
- other use
- any use
- management of drug-related select adverse event (any grade, grade 3-5) by select AE category/subcategory (EU Submission)
- management of IMAEs (any grade, grade 3-5) by IMAE category (US Submission)

will be reported separately for each treatment group (percentages of treated subjects by medication class and generic term).

For each category/subcategory of drug-related select AEs (any grade, grade 3-5) and IMAEs (any grade, grade 3-5), the following will be reported for each treatment group:

• The total immune modulating medication treatment duration (excluding overlaps), duration of high dose of corticosteroid, initial dose of corticosteroid, and tapering duration (summary statistics)

Duration represents the total duration the subject received the concomitant medication of interest. If the subject took the medication periodically, then DURATION is the summation of all use. Initial dose represents the dose of the concomitant medication of interest received at the start of the event. In the case multiple medications started on the same date, the highest equivalent dose is chosen and converted to mg/kg by dividing by the subject's recent weight.

These analyses, except the ones related to IMAEs will be conducted using the 30-day safety window. The analyses related to IMAEs will be conducted using the 100-day safety window.

# 7.4.3.2 Subsequent Cancer Therapy

Number and percentage of subjects receiving subsequent cancer therapies will be summarized for all randomized subjects. Categories include:

- Subsequent systemic therapy
- Subsequent surgery for treatment of tumors
- Subsequent radiotherapy for treatment of tumors

A by-subject listing of subsequent cancer therapy will also be produced for all randomized subjects.

# 7.5 Efficacy

Principal analyses of progression free survival (PFS) and objective response rate (ORR) will be based on the Blinded Independent Central Review (BICR) evaluation, unless noted otherwise.

Analyses in this section will be tabulated for all randomized subjects by treatment group as randomized, unless otherwise specified.

Unless stated otherwise, whenever a stratified analysis is specified, the following stratifications factors (recorded at randomization as per IRT) will be used:

- Tumor cell PD-L1 status (expressing  $[\ge 1\%]$  vs non-expressing [< 1%] or non-evaluable).
- HPV p-16 status (oropharyngeal HPV p-16 positive vs oropharyngeal HPV p-16 negative or non-oropharyngeal).
- Prior chemotherapy (adjuvant/neoadjuvant/multimodal treatment) status (Yes/No).

For assessing the secondary objectives of this study except to compare the OS of subjects with  $PD-L1\ CPS \ge 1$  between treatment groups, no testing procedure will be used.

Confidence intervals (CI) for primary endpoint analyses will be based on nominal significance level adjusted for primary endpoints and interim analyses to preserve overall type one error rate.

Alpha ( $\alpha$ ) for the CI will be the same as nominal significance level for hypothesis testing. CIs for other endpoints will be at the two-sided 95% level. All p-values reported will be two-sided. P-values will be rounded to the fourth decimal place. Point estimates and confidence bounds for efficacy variables will be rounded to the second decimal place.

A by-subject listing of efficacy results will be presented including treatment group, treatment duration, BICR progression date, overall survival, death date, etc.

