8.4.2.2 Analysis Methods for Secondary Endpoints

The analyses of OS in the randomized participants with PD-L1 CPS ≥ 1 population will be similar to those in the randomized participants with PD-L1 CPS ≥ 20 , except that testing will be contingent upon a significant result for the primary OS comparison in PD-L1 CPS ≥ 20 population. On the other hand, if the test for this secondary endpoint is significant and the initial test for OS in all randomized participants is not significant, the latter can be retested with full $\alpha = 0.05$.

The analysis of PFS in the participants with PD-L1 CPS ≥ 20 and in all randomized participants will be performed using a stratified Cox proportional hazards model with treatment arm as the sole covariate. An estimate of the hazard ratio (HR) and a corresponding two sided 95% CI for the HR will be generated. Survival distributions will be estimated, by arm, via the Kaplan-Meier (KM)

product-limit method. Median survival times along with 95% CI for the medians, will also be presented. The confidence interval for the median will be constructed using a generalization of the Brookmeyer and Crowley method based on a log $\{-\log\}$ transformation of the survival function. No statistical test will be performed.

ORR and its associated 95% CI will be presented per arm, in all randomized participants and participants with PD-L1 CPS ≥ 20 . The confidence interval for ORR will be computed using the Clopper and Pearson method. The odds ratio (OR) and 95% confidence interval for the ratio will be generated using the Cochran-Mantel-Haenszel (CMH) method.

The distribution of DOR will be estimated via the KM method for participants whose best response is PR or CR, by arm. Medians and 6, 9, and 12 month rates will also be estimated. These analyses will be conducted on the all randomized population and PD-L1 CPS ≥ 20 subpopulation.

No statistical test will be performed for ORR, DOR for all randomized participants and participants with PD-L1 CPS ≥ 20 .

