#### APPENDIX 4 SEQUENTIALLY REJECTIVE PROCEDURE

Section 7.5.6 of this SAP specifies the multiple testing procedure that controls family-wise type I error rate of 5% in the strong sense across primary and secondary endpoints. After rejecting an individual hypothesis, the local significance levels and the transition weights of the edges are updated: the rules for that update are determined by Algorithm 1 in Maurer and Bretz (2013). The resulting sequentially rejective testing procedure is uniquely determined by the graph in Figure 7.5.6-1. Below example illustrates the principles of this iterative procedure.

In this study, two primary endpoints (OS in all randomized subjects and OS in subjects with PD-L1 CPS  $\geq$  20) and one secondary endpoint (OS in subjects with PD-L1 CPS  $\geq$  1) will be tested at the interim analysis (Time 1) and final analysis (Time 2) as described in Section 5.

[figure not shown]
Step 1: At Time 1, OS in all randomized subjects and OS in subjects with PD-L1 CPS  $\geq$  20 will be respectively tested in nominal alpha 0.01 (obtained from O'Brien and Fleming  $\alpha$ -spending function given information fraction of 80% and initial overall alpha is equally split for the two endpoints). Assuming only OS in subjects with PD-L1 CPS  $\geq$  20 is rejected, it will be removed from the graph and the entire nominal alpha (0.025) for this endpoint will be passed to the secondary endpoint OS in subjects with PD-L1 CPS  $\geq$  1. The below figure illustrates the update of the graph before (part A) and after (part B) Step 1.

Step 2: At Time 1, OS in subjects with PD-L1 CPS  $\geq$  1 will be tested at 0.01 (the nominal alpha is determined by the actual information fraction for this population and can vary from 0.01). If it is not significant, graph will not change and continue to Step 3.

Step 3: At Time 2 (final analysis), OS in all subjects and in subjects with PD-L1 CPS  $\geq$  1 will each be tested at 0.022. Assuming only OS in subjects with PD-L1 CPS  $\geq$  1 is rejected, it will be removed from the graph and the entire nominal alpha (0.025) for this endpoint will be passed to

the endpoint OS in all randomized subjects. The below figure illustrates the update of the graph before and after Step 3.

Step 4: The overall alpha for OS in all randomized subjects becomes 0.05 and this endpoint can be retested with nominal alpha of 0.043 at Time 2 (final analysis).

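### SAP 7.5, read literally, gives OS in CPS ≥1 a 95% confidence interval although it is tested at a stricter level, so the interval can exclude 1 when the test fails

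*SAP*

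**What the plan says.** SAP 7.5 sets the confidence levels for the efficacy section. It first rules out testing for the secondary objectives, with one exception: "For assessing the secondary objectives of this study except to compare the OS of subjects with" CPS ≥1. It then states: "Confidence intervals (CI) for primary endpoint analyses will be based on nominal significance level adjusted for primary endpoints and interim analyses". For everything else the rule is "CIs for other endpoints will be at the two-sided 95% level".

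SAP 4.2.1 lists OS in CPS ≥1 among the secondary endpoints, and SAP Appendix 4 describes the graph as covering two primary endpoints "and one secondary endpoint (OS in subjects with PD-L1 CPS" ≥1). In the worked example there, CPS ≥1 is tested at about 0.01 at the interim, where "the nominal alpha is determined by the actual information fraction for this population and can vary from 0.01". At the final analysis CPS ≥1 and all randomized subjects "will each be tested at 0.022". The closing paragraph of Appendix 4 gives CPS ≥1 an overall alpha of 0.05 if both primary hypotheses are rejected.

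Protocol 8.4.2.1 sets the level of the OS hazard ratio interval from the nominal level of the group sequential log-rank test. Protocol 8.4.2.2 says OS in CPS ≥1 is analysed like OS in CPS ≥20, with one stated exception: "testing will be contingent upon a significant result for the primary OS comparison" in CPS ≥20. That exception concerns gatekeeping, not the confidence level. The same section names 95% for PFS and ORR but not for OS in CPS ≥1.

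SAP 7.5.6 calls for the stratified OS hazard ratio with an interval at level 1 − α, adjusted for the interim. It opens with the two primary objectives and does not name CPS ≥1 in its text.

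**The concern.** An interval reported beside a formal test should agree with it. If the test uses 0.022 and the interval uses 0.05, some observed hazard ratios give an interval wholly below 1 beside a p-value that misses its boundary. A reader who looks only at the interval would take the CPS ≥1 result as positive when the controlled procedure says otherwise. CPS ≥1 OS is the endpoint the protocol rationale (section 1.2) calls key secondary, and its success can pass alpha back to OS in all randomized subjects, so its status needs to be unmistakable. The SAP also appears to depart from the protocol here without saying so.

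**Working it through.** **Inputs.** Deaths in CPS ≥1: 505 at interim, 632 at final (SAP 5, after Table 5-1). Allocation 1:1 (SAP 2.1). O'Brien-Fleming alpha spending, overall two-sided alpha 0.025, or 0.05 if both primary hypotheses are rejected (SAP 7.5.6, Appendix 4). The standard error of the log hazard ratio is taken as 2/√d, where d is the number of deaths.

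**Step 1: reproduce the plan's levels.** Information fraction t = 505/632 = 0.799. With one-sided alpha 0.0125, the Lan-DeMets O'Brien-Fleming spend at t is 2[1 − Φ(2.498/√0.799)] = 0.0052, that is 0.0104 two-sided (z = 2.562). The final bound solves P(Z1 ≥ 2.562 or Z2 ≥ z2) = 0.0125 with correlation √0.799. This gives z2 = 2.292, two-sided 0.0219. Both round to the 0.01 and 0.022 in Appendix 4. With overall alpha 0.05 the levels are 0.0243 and 0.0429 (z = 2.252 and 2.025). The latter matches the 0.043 that Appendix 4 gives for all randomized subjects.

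The same method gives critical hazard ratios of 0.810/0.845 (all randomized) and 0.744/0.788 (CPS ≥20). SAP Table 5-1 states 0.81/0.845 and 0.74/0.788.

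**Step 2: where test and interval disagree.** The test succeeds if the observed HR is at or below exp(−2z/√d). A 95% interval excludes 1 if the HR is below exp(−2 × 1.960/√d).

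| Overall alpha | Look | Deaths | z | HR needed by test | HR at which 95% CI excludes 1 | Contradictory range |
|---|---|---|---|---|---|---|
| 0.025 | Interim | 505 | 2.562 | 0.796 | 0.840 | 0.796–0.840 |
| 0.025 | Final | 632 | 2.292 | 0.833 | 0.856 | 0.833–0.856 |
| 0.05 | Interim | 505 | 2.252 | 0.818 | 0.840 | 0.818–0.840 |
| 0.05 | Final | 632 | 2.025 | 0.851 | 0.856 | 0.851–0.856 |

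**Step 3: interval widths.** On the log scale the matched interval is wider than the 95% interval by 2.562/1.960 = 1.31 (interim) and 2.292/1.960 = 1.17 (final) with overall alpha 0.025. The matching confidence levels are 98.96% and 97.81%. With overall alpha 0.05 they are 97.57% and 95.71%.

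**Step 4: an example.** Final analysis, 632 deaths, observed HR 0.845. SE = 2/√632 = 0.0796; |ln 0.845|/SE = 0.1684/0.0796 = 2.12; p = 0.034. The test fails at 0.022. The 95% interval is 0.72–0.99; the matched interval is 0.70–1.01.

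**Step 5: how often.** The chance that Z falls between 1.960 and the boundary at a single look, with overall alpha 0.025 and under proportional hazards, depends on the true hazard ratio. At the SAP's average HR of 0.70 it is 5.4% (interim) and 0.8% (final). For assumed values of 0.80 and 0.85 it is 23% and 10.5%, and 22% and 13%. These figures are illustrative: they do not condition on CPS ≥20 having been rejected first, or on the result of the other look.

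**The case against.** The best counter-argument is SAP 7.5.6. It is the section on OS analysis, contains the testing hierarchy, and prescribes an adjusted interval. Appendix 4 says the procedure in 7.5.6 spans primary and secondary endpoints. No other SAP section specifies the hazard ratio analysis that accompanies the CPS ≥1 test. A reasonable statistician could therefore apply 7.5.6 to all three OS comparisons and take the other endpoints in 7.5 to be the untested ones.

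That argument stands in part. A reader might infer that the SAP unequivocally fixes a 95% interval for CPS ≥1; 7.5.6 prevents that conclusion. It does not settle the matter the other way either, because 7.5.6 is framed around the primary objectives while 7.5 confines matching to primary endpoints in explicit terms. Either interval could be programmed in good faith.

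Four further limits also stand:

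- A reader might infer inflated type I error. The documents do not support this: success is judged by the log-rank test against its boundary, and SAP 7.5.6 also reports the p-value.
- A reader might treat CPS ≥1 as a likely labelling population. Neither document says so.
- A contradiction about a failed test can arise only after CPS ≥20 has succeeded. The wider interim range matters only if interim results are released, since SAP 2.3 bars the sponsor from data by arm while the study is ongoing.
- Protocol 8.4.5 and SAP 7.8.2 ask for 95% intervals in CPS subgroups, with CPS ≥1 among the protocol's cutoffs. A change to 7.5 alone would not remove every 95% interval for CPS ≥1.

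**Conclusion.** The point holds as a reporting inconsistency. Read literally, SAP 7.5 separates the CPS ≥1 interval from its test and departs from protocol 8.4.2.1–8.4.2.2; read with 7.5.6, the SAP is ambiguous. The levels 0.010/0.022 apply when CPS ≥20 is rejected and all randomized is not. If both are rejected, the levels are about 0.024/0.043, and the final-analysis discrepancy is then slight.

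The ranges in the table assume the planned 505 and 632 deaths and SE = 2/√d. Actual event counts will shift the boundaries, and stratified Cox intervals may differ slightly. Error control, power and the testing graph are unchanged. The matter is worth correcting because it affects how the only formally tested secondary endpoint will be read.

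**What to change.** In SAP 7.5, with a cross-reference to 7.5.6, state that the hazard ratio interval for every formally tested OS endpoint (CPS ≥20, all randomized, CPS ≥1) has level 100 × (1 − nominal alpha)%, using the look and the overall alpha that actually applied. Then add:

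- If CPS ≥1 is not reached in the hierarchy it has no nominal alpha, so report a 95% interval labelled descriptive.
- Label the 95% intervals in the biomarker subgroup outputs (protocol 8.4.5, SAP 7.8.2) as descriptive.
- Keep 95% for endpoints that are not tested.

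This needs a few sentences and no new data. The cost is a wider CPS ≥1 interval: by 1.31 (interim) or 1.17 (final) on the log scale with overall alpha 0.025, and by 2.252/1.960 = 1.15 or 2.025/1.960 = 1.03 with overall alpha 0.05.

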# 7.5.1 Analysis of Objective Response Rate

One of the objectives of the study is to estimate the ORR per BICR in the treatment groups among all randomized subjects.

The number and percentage of subjects in each category of BOR per BICR (complete response [CR], partial response [PR], stable disease [SD], progressive disease [PD], or unable to determine [UTD]) will be presented, by treatment group. Estimates of response rate, along with its exact two-sided 95% CI by Clopper and Pearson will be presented, by treatment group.

Similar analyses will be repeated based on the investigator's assessment of ORR. A cross tabulation of BICR best response versus the investigator best response will be presented, by treatment group and by response categories. Concordance Rate of Responders will be computed as the frequency with which investigator and BICR agree on classification of a subject as responder vs. non responder/UTD as a proportion of the total number of randomized subjects assessed by both the investigator and BICR.

The following subject-level graphics will also be provided:

- For the responders only, time courses of the following events of interest will be graphically displayed: tumor response.
- For response evaluable subjects (randomized subjects with baseline and at least one on-study tumor assessment),
  - A bar plot showing the best % reduction from baseline in sum of diameter of target lesions based on BICR assessment for each subject will be produced (excluding assessments after PD and assessments after start of subsequent anti-cancer therapy).
  - A plot of individual time course of tumor burden change per BICR assessment will be produced.

A by-subject listing of best overall response will be presented including treatment group, best overall response per BICR and dates of CR/PR/progression.

A by-subject listing of per time point tumor response per BICR will be presented.

# 7.5.2 Time to Tumor Response and Duration of Response

Duration of response (DOR) and time to response (TTR) will also be evaluated for subjects who achieved confirmed PR or CR. The DOR for each treatment group will be estimated using the Kaplan-Meier (KM) product limit method and will be displayed graphically. A table will be produced presenting number of events, number of subjects involved, medians, and 95% CIs for the medians. Median values of DOR, along with two-sided 95% CI in each treatment group will be computed based on a log-log transformation method.

The status of subjects who are censored in the DOR KM analysis will be tabulated for each treatment group including the following categories:

• Ongoing follow-up (current [last scan within adequate window vs cutoff date], not current)

- Off-study (lost to follow-up, withdraw consent, never treated)
- Received subsequent anticancer therapy.

TTR, which does not involve censoring, will be summarized by treatment group in all responders using descriptive statistics.

A by-subject listing will be presented including treatment group, best response, time to response, duration of response, whether the subject was censored for duration of response, and, if so, the reason.

# 7.5.3 Analysis of DCR

Similar to ORR analysis, BICR-determined DCR in arm A and B will be estimated and its corresponding 95% exact two-sided CIs will be calculated using the Clopper Pearson method. This analysis will also be performed for DCR as assessed by the investigators.

# 7.5.4 Analysis of Progression-Free Survival

The PFS function for each treatment group will be estimated using the KM product limit method and will be displayed graphically. A two-sided 95% CI for median PFS in each treatment group will be computed via the log-log transformation method. PFS rates at fixed time points (e.g. 6 months, depending on the minimum follow-up) will be presented along with their associated 95% CIs. These estimates will be derived from the Kaplan Meier estimate and corresponding CIs will be derived based on Greenwood formula for variance derivation and on log-log transformation applied on the survivor function.

The estimate of the PFS hazard ratio between treatment groups will be calculated using a stratified Cox proportional hazards model, with treatment as the sole covariate. A two-sided 95% CI for the hazard ratio will also be presented. Further, the estimate of the PFS hazard ratio based on weighted logrank test may be provided.

Analyses of PFS will be conducted based on the primary definition and secondary definition of PFS.

The source of PFS event (progression or death) will be summarized by treatment group. The status of subjects who are censored (as per primary definition of PFS) in the PFS KM analysis will be tabulated for each treatment group including the following categories:

- On-study (on-treatment, in follow-up)
- Off-study (lost to follow-up, withdraw consent, never treated)
- No baseline tumor assessment
- No on-study tumor assessment and no death
- Received subsequent anticancer therapy

A by-subject listing will be presented including treatment group, PFS duration under the primary definition, PFS duration on the ITT definition, whether the subject was censored under the primary definition, and if censored, the reason, and whether the subject was censored under the ITT definition, and if censored, the reason.

A by-subject listing of lesion evaluations per BICR will be presented.

# 7.5.5 Supportive Analyses of Progression-Free Survival

The following sensitivity analyses will be conducted using both the primary and the secondary definition of PFS in all randomized subjects:

[figure not shown]
- A cross tabulation of PFS assessment by BICR versus PFS assessment by investigator will be
  presented, by treatment group. Concordance Rate of event will be computed as the frequency
  with which investigator and BICR agree on classification of a subject as event vs censored as
  a proportion of the total number of randomized subjects assessed by both the investigator and
  BICR.
- A by-subject listing of PFS assessment per BICR and investigator will be presented.

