#### 2 STUDY DESCRIPTION

#### 2.1 Study Design

Protocol CA209651 is a randomized open-label, Phase 3 trial in subjects ≥ 18 years old with untreated metastatic or recurrent SCCHN that is not amenable to curative therapy, evaluating nivolumab + ipilimumab versus the EXTREME regimen (cetuximab + cisplatin/carboplatin + fluorouracil) as a first-line treatment.

Subjects will undergo screening evaluations to determine eligibility prior to randomization. Approximately 930 subjects will be randomized to the two treatment arms in a 1:1 ratio and stratified by the following factors:

• Tumor cell PD-L1 status (expressing [≥ 1%] vs non-expressing [< 1%] or non-evaluable). Up to 10% of randomized subjects per cohort can be included into the study as "non-evaluable." After this point, subjects with non-evaluable results will not be permitted to be randomized; the site would need to submit an additional tumor tissue for testing with either a result of "expressing" or non-expressing" in order to randomize the subject.

- HPV p-16 status (oropharyngeal HPV p-16 positive vs oropharyngeal HPV p-16 negative or non-oropharyngeal).
- Prior chemotherapy (adjuvant/neoadjuvant/multimodal treatment) status (Yes/No)

The dose and treatment schedules for each arm are as follows:

- Arm A: Nivolumab + Ipilimumab Arm:
  - Nivolumab 3 mg/kg IV every 2 weeks + Ipilimumab 1 mg/kg IV every 6 weeks until progression, unacceptable toxicity, or a maximum of 24 months from first study treatment.
- Arm B: EXTREME regimen Arm:
  - Cetuximab 400 mg/m² IV for the initial dose only, then 250 mg/m² weekly + cisplatin (100 mg/m²) or carboplatin (AUC of 5 mg per milliliter per minute) on Day 1 and fluor-ouracil (1000 mg/m² per day for 4 days) every 3 weeks for maximum of 6 cycles followed by maintenance cetuximab at 250 mg/m² weekly (or every 2 weeks, per local prescribing information) until disease progression or unacceptable toxicity; the choice of cisplatin or carboplatin is at the discretion of the investigator.

Tumor progression or response will be assessed by investigator using RECIST 1.1 criteria. Treatment with study medication will continue until RECIST 1.1 defined progression, unacceptable toxicity, a maximum of 24 months from the first study treatment, or withdrawal of consent.

Dose reductions will be not be allowed for nivolumab or ipilimumab.

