# 4.2.2.2 Secondary Definition of Progression Free Survival (Irrespective of Subsequent Therapy)

The secondary definition of PFS (ITT definition) is defined as the time between the date of randomization and the date of first documented tumor progression, based on BICR assessments (per RECIST v1.1 criteria), or death due to any cause, whichever occurs first. Figure 4.2.2.2-1 show the graphic display of secondary definition of PFS.

Subjects who die without a reported progression will be considered to have progressed on the date of their death. The following censoring rules will be applied for the secondary definition of PFS:

- Subjects who did not progress or die will be censored on the date of their last evaluable tumor assessment.
- Subjects who did not have any on study tumor assessments and did not die will be censored on their date of randomization.

Censoring rules for the secondary definition of PFS (ITT definition) are presented as follows and in Table 4.2.2.2-1.

Figure 4.2.2.2-1: PFS Secondary Definition

[figure not shown]

Table 4.2.2.2-1: Censoring Scheme for Secondary Definition of PFS

Situation	Date of Progression of Censoring	Outcome
No baseline tumor assessment	Date of randomization	Censored
No on-study tumor assessments and no death	Date of randomization	Censored
Documented progression per RE- CIST v1.1	Date of first documented progression per RECIST v1.1 criteria (excludes clinical progression)	Progressed
No progression and no death	Date of last evaluable tumor assessment	Censored
Death without progression per RE-CIST v1.1	Date of death	Progressed

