#### 5 SAMPLE SIZE AND POWER

The primary objectives of this study are to compare OS between treatment groups, in all randomized subjects and randomized subjects with PD-L1 CPS  $\geq$  20. OS will be compared at the 0.025 alpha level for each of the above two populations.

The OS comparison in all randomized subjects will require up to 741 deaths. This number of events ensures that a two-sided, alpha = 0.025 group sequential test using the O'Brien and Fleming spending function and with an interim analysis after approximately 80% of events, will have overall 97% power for a HR of 1.2 for the first 7 months and 0.55 thereafter.

Delayed separation of KM curves is included in the alternative hypotheses for OS because it was observed in CA209141, a randomized phase 3 study of nivolumab versus investigator's choice

therapy in platinum-refractory, recurrent/metastatic SCCHN and in KEYNOTE-048, a randomized phase 3 study of pembrolizumab or pembrolizumab plus chemotherapy versus cetuximab with chemotherapy in untreated recurrent/metastatic SCCHN.

The final analysis of OS in all randomized subjects is projected to occur 51 months after the first patient was randomized. An interim analysis in this population will be performed when approximately 593 deaths occur, or all randomized subjects have been followed up for at least 12 months, whichever is later. It is projected for 39 months after the first patient was randomized.

At the same time as the OS analysis is done for all randomized subjects, OS will also be compared between arms in the randomized subjects with PD-L1 CPS  $\geq$  20 population via a two-sided, alpha = 0.025 group sequential test procedure incorporating the O'Brien and Fleming alpha spending function. The group sequential test would have an interim analysis and the final analysis of OS, at which approximately 298 and 372 deaths, respectively, are expected. With this many events, the test procedure would have an overall 99% power if the HR was 1.06 for the first 7 months and 0.45 thereafter. Table 5-1 summarizes the statistical assumption and power calculation.

Table 5-1: Statistical Assumption and Power Calculation

Primary endpoints	OS for ITT (N = 930)	OS for PD-L1 CPS $\geq$ 20 (N = 465)
Median OS months (N+I/ EXTREME	13/10.8	14.9/10.8
regimen)		
Average hazard ratio	0.74	0.61
Alpha level (IA/FA)	0.01/0.022	0.01/0.022
Event Number (IA/FA)	593/741	298/372
Critical hazard ratio (IA/FA)	0.81/0.845	0.74/0.788

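### Under the secondary PFS definition, the reader concordance rate in SAP 7.5.5 is dominated by deaths and ignores when each reader dated progression

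*SAP*

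**What the plan says.** SAP 7.5.5 plans three things, under both PFS definitions and in all randomized subjects: a cross-tabulation of BICR against investigator PFS by treatment group, a concordance rate, and a by-subject listing of both assessments. The rate is the frequency "with which investigator and BICR agree on classification of a subject as event vs censored", as a proportion of the randomized subjects whom both readers assessed.

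The two definitions treat deaths differently. Under the secondary definition (SAP 4.2.2.2), "Subjects who die without a reported progression will be considered to have progressed on the date of their death", and subsequent therapy does not censor. The one exception to counting deaths is in Table 4.2.2.2-1: a subject without a baseline tumor assessment is censored at randomization. Under the primary definition (SAP 4.2.2.1), new anti-cancer therapy before documented progression censors the subject, and a later death is ignored.

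Principal PFS results use BICR (SAP 7.5), and Protocol 8.4.2.2 rules out a statistical test of PFS. SAP 7.5.1 and 7.5.3 repeat ORR and DCR by investigator. The visible text of SAP 7.5.4 and 7.5.5 has no matching investigator PFS curve or hazard ratio.

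**The concern.** The trial is open label, and treatment beyond progression is allowed in Arm A only (Protocol 4.5.6), so the timing of investigator progression calls could differ by arm. A reader of the report will look to 7.5.5 to see how far investigator and central readings agree.

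Under the secondary definition the rate says little about that. A subject who has died is an event for both readers whatever either saw on the scans. Where both flags read 'event', the two progression dates may be months apart and still count as agreement. SAP 2.6 adds to this: scans may stop only once investigator and central readers have both found progression. That moves both flags towards 'event' over time and leaves timing as the main remaining disagreement, which the rate discards.

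At stake is the interpretation of a supportive table: a high figure could be taken as reassurance about reading bias that it does not give.

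**Working it through.** **The plan's own figures.** The SAP states no expected concordance. The inputs are its sample size ("Approximately 930 subjects will be randomized to the two treatment arms in a 1:1 ratio", SAP 2.1) and its death counts ("The OS comparison in all randomized subjects will require up to 741 deaths" and "approximately 593 deaths occur" for the interim, SAP 5). The counts are coherent. With O'Brien-Fleming spending of a two-sided 0.025 at 593/741 = 0.800 of the information, the nominal levels are 0.0105 and 0.0219 (stated 0.01 and 0.022) and the critical hazard ratios 0.810 and 0.845 (stated 0.81 and 0.845). Overall power at the tabulated average hazard ratio of 0.74 is 96.6% (stated 97%).

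**Death floor, secondary definition.** Floor = deaths / subjects in the denominator. If both readers assessed all 930:

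- final: 741/930 = 79.7%
- interim count: 593/930 = 63.8%

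If the table were repeated in CPS ≥ 20 (N = 465, "at which approximately 298 and 372 deaths, respectively, are expected"), the floors are 372/465 = 80.0% and 298/465 = 64.1%. Agreement by coin flip among survivors would give 0.797 + 0.203 × 0.5 = 90% and 0.638 + 0.362 × 0.5 = 82%.

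**Effect of the denominator.** The SAP does not say how many subjects both readers will assess. If u are not assessed by both, the final floor runs from (741 − u)/(930 − u), all of them dead, to 741/(930 − u), all of them alive:

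| Assumed share unassessed | u | Floor at 741 deaths |
|---|---|---|
| 2% | 19 | 79.3% to 81.3% |
| 5% | 46 | 78.6% to 83.8% |
| 10% | 93 | 77.4% to 88.5% |

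**Simulation, to show direction only.** Assumed: 930 patients, 300 replicates, uniform 26-month accrual, cutoff at 51 months, control median OS 10.8 months with the planned hazard ratios of 1.2 and then 0.55, exponential time to progression with median 6.5 months in both arms, and progression seen at 6-weekly scans. About 85% are dead at cutoff, against the planned 79.7%.

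*Dating bias only.* Control-arm investigator progression is dated early, and 50% start new therapy 0.7 months after investigator progression:

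| Shift | BICR HR (secondary) | Investigator HR (secondary) | Concordance, secondary | Concordance, primary |
|---|---|---|---|---|
| about 6 weeks | 1.01 | 0.90 | 100% | 87.7% |
| about 12 weeks | 1.00 | 0.80 | 100% | 86.8% |

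*Complete disagreement.* BICR confirms no investigator progression, and there is no date shift. Secondary-definition concordance is still 85%, which is the death share. Primary-definition concordance falls to 64% or 51% when 50% or 80% start new therapy.

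The primary-definition rate therefore moves, but only because new therapy censors the BICR record before BICR progression is reached. The size of the drop depends on how many patients start new therapy and how soon. A shift in which BICR progression still precedes new therapy leaves the rate unchanged.

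**The case against.** The strongest reply is that this is one of two planned runs of a descriptive table, and that several stronger readings fail.

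- A reader might infer that deaths force agreement to 80% in general. The documents do not support that. Under the primary definition a patient with investigator progression, no BICR progression, new therapy and then death is discordant. Even under the secondary definition the figure is about 64% at 593 deaths, and the denominator is the subjects assessed by both readers, not 930.
- A reader might infer that differential early calling by arm cannot be detected at all. That is also too strong. The cross-tabulation is by treatment group, so an arm difference in event/censored disagreement is visible, and the primary-definition rate can fall when early calls lead to new therapy. What stays hidden under the secondary definition is timing.
- A reader might infer that a planned result is biased. The shifted hazard ratios above are investigator estimates that the visible text does not plan to report; the secondary-definition BICR hazard ratio stayed at 1.00 to 1.01. The SAP nowhere calls the rate its check on investigator bias. Central blinded reading is the main protection.
- A reader might extend the point to ORR, where SAP 7.5.1 counts how often the readers "agree on classification of a subject as responder vs. non responder/UTD". The best-response cross-tabulation planned there by arm allows a chance-corrected measure to be calculated, so nothing need be added.

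These limits stand. Two others should be noted: a figure in SAP 7.5.5 is not shown in the public text, and the table mock-ups are in a Data Presentation Plan that is not public. The by-subject listing may also show dates, but the SAP does not say so and plans no summary of it. None of this alters the main fact that the stated rate takes only two flags as input.

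**Conclusion.** The point holds for the secondary definition. Deaths alone set agreement at about 80% at 741 deaths and about 64% at 593. With an assumed 2% to 10% of subjects not assessed by both readers, the final floor lies between 77% and 89%. Because no dates enter the rate, a timing shift that leaves the flags unchanged is invisible to it; that follows from the definition and does not rest on the simulation. The simulated hazard ratios and primary-definition rates rest on the assumptions listed and show direction, not predicted values.

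Under the primary definition there is no death floor, and any sensitivity to early calls comes through censoring. The consequence is confined to the interpretation of a descriptive secondary endpoint. The OS comparisons, where "OS will be compared at the 0.025 alpha level for each of the above two populations", are unaffected. This is an inexpensive improvement, not a flaw in the trial's main inference.

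**What to change.** In SAP 7.5.5, alongside the planned cross-tabulation:

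1. Compute agreement on documented RECIST progression, excluding death, and count it as agreement only when the two dates fall within one scheduled scan interval (6 weeks to week 48, 12 weeks thereafter). State the denominator, for example subjects with documented progression by at least one reader.
2. Report the early and late discrepancy rates by arm, with the between-arm difference.
3. Present the investigator-assessed PFS hazard ratio beside the BICR one, in line with what 7.5.1 and 7.5.3 already do for ORR and DCR.

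The cost is SAP wording and one extra table from data already collected. The downside is that the reported agreement figures will be lower.
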